- Circumstances may arise (e.g., pandemic, natural disaster, political upheaval, or to minimize subject and caregiver burden) when on-site assessments of efficacy and/or safety are not possible. In those cases, assessments may be performed offsite by raters either in person, or via video technology or telephone where possible. Remote visits are permitted for Week 2 (Visit 4) and Week 5 (Visit 7). For all other visits that are conducted remotely, the Investigator must contact the Medical Monitor for approval of the plan. Sites must keep a log to identify details of all visits that are administered remotely. Provided that the subject is physically in the clinic, and accompanied by a relative, all caregiver-rated assessments may be provided remotely.
- All assessments must be completed and subject must meet required eligibility criteria before being randomized.
- Subjects will be assessed for their ability to swallow a test capsule (i.e., placebo). If the subject is unable to swallow a test capsule at the Screening visit, they may take some capsules home to practice, and will be re-assessed at the Baseline visit.
- 12-lead ECGs should be performed in sequential triplicate. Electrocardiograms should be performed before blood sampling or at least 30 minutes after blood sampling. The subject must rest in a sitting or supine position for 5 minutes before the ECG is obtained. One repeat set of triplicate ECGs is allowed that can occur either at Screening or Baseline.
- Mild sedation is allowed exceptionally for ECGs and blood draws during the study (e.g., alprazolam at a pediatric-appropriate dose per age, and the lowest dose deemed necessary by the Investigator) just in cases when the subject's agitation/anxiety does not allow a safe and accurate measurement and the Investigator, with agreement from the caregiver, considers it safe and appropriate for the subject.
- For all PK samples (scheduled and unscheduled, and except at the Baseline visit) the dates and times of administration of the last three doses of the study drug should be recorded.
- At the Baseline visit, a PK sample is drawn predose.
- Every effort should be made to collect a PK sample at an unscheduled visit because of an SAE, or an AE leading to discontinuation.

Final Version: 1.0 Date: 21 December 2022

For female subjects of childbearing potential, a serum pregnancy test will be completed at the Screening visit; urine pregnancy dipstick tests will be completed at all other scheduled timepoints.

- A urine toxicology dipstick should be used in addition to the urine toxicology screen at both the Baseline visit and Visit 8 (to confirm eligibility in Study ACP-103-070). A rapid UDS dipstick will be used at Visit 3.
- Study drug may be dispensed to the subject at unscheduled visits if needed.
- If visit is remote, accountability will be assessed verbally with the caregiver, and verified at the next clinic visit.
- The involvement of experienced personnel in the conduction of routine procedures such as blood drawing and ECG recording in this population is strongly recommended.
- The ET visit will not be done if the subject withdraws consent to participate in all parts of the study and withdrawal of consent happens before that timepoint.
- Prolactin results should be blinded to the Investigator and the Sponsor after Baseline. Results will be monitored by an independent Medical Monitor from the Contract Research Organization (CRO).
- Including COVID-19 vaccination.
- For scales that require caregiver input, the caregiver should be the parent/LAR or designee. A designee should be a family member, adult and responsible, living with or in very frequent contact with the subject participating in the study, that is committed to providing responses for the caregiver-reported scales for the duration of Studies ACP-103-069 and ACP-103-070. Caregivers providing input for the ABC, RBS-R, and CGSO scales will be trained in accurate symptom reporting (ASR) prior to completing the scales. The ASR training should be done at Screening before the caregiver completes any scales, and repeated whenever there is a change in caregiver or if the site feels a caregiver requires retraining.
- If visit is conducted remotely, vital signs, height, weight, and BMI are optional.
- As measured by stadiometer.
- The ESRS-A will only be conducted at clinic visits and not at remote visits.
- If the caregiver reports an occurrence of syncope, the investigator should ask the "syncope adverse event questions", as a tool to guide diagnosis, in Appendix G.
- If the caregiver reports an occurrence of somnolence, the investigator should ask the "somnolence adverse event questions", as a tool to guide diagnosis, in Appendix H.

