Safety results will be summarized by treatment group using descriptive statistics in the Safety Analysis Set. No formal statistical testing will be performed for any of the safety endpoints. Adverse events will be classified into standard terminology using the Medical Dictionary for Regulatory Activities (MedDRA). Treatment-emergent adverse events (TEAEs), TEAEs leading to discontinuation, TEAEs related to study drug, TEAEs by maximum severity, fatal TEAEs, serious TEAEs, and serious TEAEs related to study drug will also be summarized.

Descriptive statistics for ECGs, vital signs, weight, BMI, ESRS-A and clinical laboratory parameters, including changes from Baseline, will be tabulated by timepoint. Additionally, categorical analyses will be conducted on the incidence of subjects with prolonged QTc intervals and changes in QTc intervals in accordance with International Council for Harmonisation (ICH) guidelines.

For the C-SSRS, the number and percentage of subjects with suicidal ideation or behavior during the study will be tabulated.

An independent data and safety monitoring board (DSMB) will review interim safety data including data on TEAEs and serious TEAEs and safety laboratory data.

Pharmacokinetic Analyses

Plasma concentration data for pimavanserin, and its major metabolite (AC-279), will be listed and summarized using descriptive statistics.

Population Pharmacokinetic Analyses

[figure not shown]
Pimavanserin exposure parameters such as, but not limited to, C_{max} and AUC, will be estimated using a population PK approach.

Pharmacokinetic/Pharmacodynamic Analyses

Using appropriate PK/PD analyses, exposure-response relationships for efficacy and safety endpoints will be evaluated.

Date 21 December 2022

Figure S–1 Schematic of Study Design for ACP-103-069

Abbreviations: ASD=autism spectrum disorder; EOT=end of treatment; ET=early termination; yrs=years

Subjects who complete the 6-week Treatment Period may be eligible to enroll in a 52-week, open-label extension study (Study ACP-103-070). Subjects entering ACP-103-070 will not complete a follow-up telephone call as they will be immediately enrolled in ACP-103-070.

Table S-1 Schedule of Events and Assessments for ACP-103-069

Period Screening			Double-blind treatment period							
		Baseline						EOT/ET ^r	Unscheduled ^a	Safety follow-up ^b
Visit Week	-4 to 0	0	1	2	3	4	5	6		10
Visit number	1	2	3	4	5	6	7	8		9
Visit window (days)	+7°		±3 ^d	±3 ^d	±3 ^d	±3 ^d	±3 ^d	±3 ^d		+3 ^d

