6.4 Safety Assessments

As known potential class side effects of antipsychotics, the following adverse events will be actively monitored, including hyperglycemia, leucopenia/neutropenia/agranulocytosis, orthostatic hypotension/bradycardia/syncope, QTc prolongation, akathisia and other extrapyramidal symptoms, weight gain, and somnolence. Criteria for identifying potentially clinically important laboratory values, ECG values, and vital signs are presented in Appendix C, Appendix D, and Appendix F, respectively; and criteria for identifying additional ECG measurements of potential clinical relevance for Medical Monitoring purposes are presented in Appendix E.

Circumstances may arise (e.g., pandemic, natural disaster, political upheaval, or technical issues) when on-site assessments of safety measures may not be possible. In those cases, assessments may be performed at the subject's place of residence either in person or via video technology or telephone, where possible. If a subject is unable to come to the site for lab draws and the site is unable to travel to the subject's place of residence, the subject may visit a local lab to obtain all safety labs. The Investigator must contact the Medical Monitor for approval with the plan. Sites must keep a log to identify details of all visits that are administered remotely.

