9.5.3.1 Treatment-emergent Adverse Events

All AEs will be coded using the Medical Dictionary for Regulatory Activities (MedDRA) coding dictionary. All AEs will be listed and treatment-emergent adverse events (TEAEs) will be summarized by system organ class and preferred term. A TEAE is defined as an AE that started after first study dose administration and no later than last study dose date + 30 days. TEAEs leading to discontinuation, TEAEs related to study drug, TEAEs by maximum severity, fatal TEAEs, serious TEAEs, and serious TEAEs related to study drug will also be summarized.

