14.1 Adverse Events

All Adverse events (AEs) will be coded using MedDRA version 24.0 or higher.

An AE (classified by preferred term) will be considered a treatment-emergent AE (TEAE) if it starts after the first study dose administration and no later than last study dose date + 30 days. AEs reported on Day 1 based on Baseline (pre-dose) findings (e.g. clinically significantly abnormal vital signs, laboratory test results, or electrocardiogram parameters) will not be considered as TEAEs.

The event counts and the number and percentage of subjects reporting TEAEs in each treatment group, and the two pimavanserin groups combined will be tabulated by SOC and preferred term; and, by SOC, preferred term, and maximum severity. If more than one AE occurs with the same preferred term for the same subject, the subject will be counted only once for that preferred term using the most severe and more related occurrence for the summarization by severity and by relationship to study drug, respectively. The display in these tables will be sorted alphabetically by SOC, and then by frequency of the two pimavanserin groups combined within each SOC.

The event counts and the number and percentage of subjects with any TEAEs will also be tabulated by preferred term without SOCs within each treatment group and sorted by frequency of the two pimavanserin groups combined.

The incidence of most frequently reported (preferred terms reported by $\geq 5\%$ of subjects in any treatment group) TEAEs, TEAEs leading to discontinuation, TEAEs related to study drug, TEAEs by maximum severity, fatal TEAEs (i.e., events that cause death), serious TEAEs, and serious TEAEs related to study drug, will be summarized by SOC, preferred term, and treatment group. In addition, TEAEs by SOC, preferred term, and stimulant use will be summarized.

Version 3.0

29 July 2024

The relationship of selected AEs to COVID-19 will be assessed as detailed in the GSD and provided in the listing. Additional summaries of relationship to COVID-19 may be provided.

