14.6 Syncope and somnolence

Syncope and somnolence are assessed at Screening and Baseline, at all visits from Week 1 through Week 6, and at unscheduled visits. Occurrences syncope and somnolence should be reported as adverse events.

Subject history of syncope, family history of syncope, subject history of somnolence will be summarized as Baseline Disease Characteristics. Incidences of syncope and somnolence during the study will be summarized as TEAEs.

Assessment of syncope and somnolence at each visit will be listed.

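### Protocol 6.4 monitors grouped class effects, but adverse events are counted only by organ class and single preferred term, so no table gives the per-child incidence of a group; the gap is sharpest for orthostatic hypotension/bradycardia/syncope

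*Protocol*

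**What the plan says.** Protocol 6.4 commits the trial to looking for specific harms: "the following adverse events will be actively monitored, including hyperglycemia, leucopenia/neutropenia/agranulocytosis, orthostatic hypotension/bradycardia/syncope, QTc prolongation, akathisia and other extrapyramidal symptoms, weight gain, and somnolence". Three of the seven items are written as groups: the white-cell item, the orthostatic hypotension/bradycardia/syncope item, and akathisia with other extrapyramidal symptoms.

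The analysis sections use a different unit.

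- Protocol 9.5.3.1: "treatment-emergent adverse events (TEAEs) will be summarized by system organ class and preferred term". The further summaries named there and in the synopsis ("TEAEs related to study drug, TEAEs by maximum severity, fatal TEAEs, serious TEAEs, and serious TEAEs related to study drug will also be summarized") are subsets of the same counts.
- SAP 14.1: counts for each arm and for "the two pimavanserin groups combined will be tabulated by SOC and preferred term", with no frequency cut-off, plus a table by preferred term alone. A further summary of the most frequent events keeps only preferred terms that reach 5% of subjects in any treatment group.
- SAP 14.6: "Incidences of syncope and somnolence during the study will be summarized as TEAEs". This sends both events to the SAP 14.1 tables.

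Neither document defines a standard MedDRA query, a custom term list or a special-interest summary. Safety is descriptive throughout (Protocol 9.5.3, SAP 14).

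**The concern.** A reader who wants to know whether more children had an orthostatic or syncopal event on high dose than on placebo needs one number per arm: children with at least one event in the group. The planned tables do not give it. Preferred-term rows cannot be added up, because a child with two terms would count twice. An organ-class row gives the group only if all its terms fall in one class and nothing else in that class is counted. The 5% summary looks at each term alone, so a group made up of several uncommon terms may not appear in it.

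At stake is a clear comparison with placebo, and across doses, for harms the protocol singles out. Protocol 1.5.1 says that pimavanserin has not been studied as monotherapy in children and adolescents, so this trial's tables will be a main source. If the grouping is first chosen after unblinding, it is open to the charge of being post hoc.

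**Working it through.** **Arm size.** Protocol 9.3 assumes a difference of 5, an SD of 10, two-sided 0.05 and 80% power. With the noncentral t distribution, power is 79.5% at 63 per arm and 80.1% at 64. Allowing for 15% discontinuation, 64 / 0.85 = 75.3, which rounds up to 76; 3 × 76 = 228. The plan's figures reproduce.

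**What 5% means.** 0.05 × 76 = 3.8, so a term needs 4 children (4/76 = 5.3%); 3 children (3.9%) do not qualify. The same threshold of 4 holds for any arm size from 61 to 80, so a few untreated subjects would not change it.

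**How large a group can be with no term in the summary.** Two terms with 3 different children each: 6/76 = 7.9%. Three terms: 9/76 = 11.8%.

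**How likely this is.** The documents give no expected event rates, so the group rate g and its split are assumptions. Take k equally frequent, mutually exclusive terms.

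- One arm, separate terms: P(no term reaches 4) is the sum of the multinomial probabilities with n = 76 and cell probability g/k per term, over all counts from 0 to 3 in each term.
- Both active arms at the same rate: the square of that, since the arms are independent.
- One grouped count in one arm: binomial P(X ≤ 3), with n = 76 and probability g.

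| Group rate, terms | One arm | Both active arms | Grouped count, one arm |
|---|---|---|---|
| 8%, three | 62% | 38% | 13% |
| 10%, three | 42% | 17% | 5% |
| 12%, three | 25% | 6% | 1.5% |
| 12%, four | 41% | 17% | 1.5% |
| 15%, three | 9% | 1% | 0.2% |

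The even split is unfavourable to the plan. With a 60/20/20 split over three terms, the one-arm figures are 28% (10% rate) and 15% (12% rate), and the both-arm figures 8% and 2%. Overlap between terms would also lower them.

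**What other analyses cover.**

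| Item in Protocol 6.4 | Other planned analysis |
|---|---|
| QTc prolongation | QTcF categories and PCI counts (SAP 14.4) |
| Akathisia and extrapyramidal symptoms | ESRS-A total and four global severity scores (SAP 14.7.2) |
| Weight gain | Change of 7% or more (SAP 14.3) |
| Hyperglycemia | Glucose and HbA1c PCI (SAP 14.2.1.3) |
| Leucopenia, neutropenia | Leukocyte and neutrophil PCI (SAP 14.2.1.3) |
| Bradycardia | Pulse PCI (SAP 14.3), ECG heart rate (SAP 14.4) |
| Orthostatic hypotension, syncope | No orthostatic criterion; syncope as a TEAE and in a by-visit listing (SAP 14.6) |
| Somnolence | As a TEAE and in a by-visit listing (SAP 14.6) |

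For orthostatic hypotension the back-up is thin. The vital-sign PCI criteria (Protocol Appendix F, SAP Table 4) use supine or sitting values, and Protocol 6.4.3 calls for standing readings only when symptoms are reported. Reported adverse events are therefore the main data.

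**The case against.** The strongest reply is that little is missing. As shown above, most of the listed effects have measurement-based analyses, and the PCI tables count each subject once per parameter. The 5% summary is supplementary: the full tables have no cut-off, every event is listed, and syncope and somnolence assessments are listed by visit. Protocol 6.4 separates terms with slashes but promises no composite incidence, and its active monitoring is carried out through visit-by-visit questioning (Protocol 6.4.6 and 6.4.7). Table specifications are kept in a separate document (SAP 1), which may contain groupings not visible here.

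Most of this stands, and it limits the point. A reader might infer that monitored effects go unanalysed or drop out of the report; the documents do not support that. A reader might also take 42%, 25% and 41% as the share of trials in which the group is missing from the 5% summary. Those are one-arm figures. The rule is 5% in any treatment group, so with both active arms at the assumed rate the figures are 17%, 6% and 17%, and lower still if a placebo term qualifies. Finally, one might assert that the three orthostatic-group terms lie in different organ classes. The documents do not give class assignments, and nothing here relies on them.

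What the reply does not supply is a count of children per group and arm. Neither an uncut term table nor a listing provides that.

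**Conclusion.** The point holds as a reporting gap that should be closed. Protocol 6.4 and SAP 14.1 and 14.6 use different units, and no specified output gives the once-per-child incidence of a monitored group. It matters most for orthostatic hypotension/bradycardia/syncope, where only pulse and heart rate have a systematic measurement-based analysis. For the other grouped items it is a gain in clarity rather than the filling of a hole.

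The size is illustrative. It rests on 76 children per arm, equal and mutually exclusive terms, and group rates of 8% to 15% that are assumed. What does not depend on those assumptions is that a group can reach 9/76 = 11.8% in an arm with no single term in the 5% summary. The efficacy analysis and the sample size are unaffected.

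**What to change.** Add to SAP 14.1 one descriptive table of TEAEs by monitored category in Protocol 6.4: at minimum orthostatic hypotension/bradycardia/syncope, and preferably the other multi-term categories. Fix the preferred-term list for each category before unblinding, using standard MedDRA queries where they exist. Count each child once per category, and show number and percentage by treatment group and for the two pimavanserin groups combined, regardless of the 5% cut-off. Keep the existing preferred-term tables alongside, and refer to the new table from SAP 14.6.

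The cost is a paragraph of SAP text, one table and a one-time blinded medical review of the term lists. No new data, visits or subjects are needed. The small downside is that grouped terms are less specific, which is why the single-term tables should stay.

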Appendix	k D	Criteria for Potentially Clinically Important ECG Values	.112
Appendix		Criteria for Identifying Additional ECG Measurements of Potential Clinical Relevance. To be Used for Medical Monitoring Purposes	.113
Appendix	κF	Criteria for Potentially Clinically Important Vital Signs	.115
Appendix	ς G	Syncope Adverse Event Questions.	.116
Appendix	кН	Somnolence Adverse Event Questions	.117

LIST OF TABLES

Table S–1	Schedule of Events and Assessments for ACP-103-069	25
Table 6–1	Safety Laboratory Evaluations	75
Table 6–2	Blood Collection Volume Limits in Affected Children	78
Table 6–3	Blood Collection Volumes for Safety Labs and Pharmacokinetic Samples (6- through 17-year-olds)	78
Table 6–4	Blood Collection Volumes for Safety Labs and Pharmacokinetic Samples (5-year-olds)	79
	LIST OF FIGURES	
Figure S–1	Schematic of Study Design for ACP-103-069	24

LIST OF ABBREVIATIONS AND DEFINITION OF TERMS

Term	Definition
5-HT	5-hydroxytryptamine (serotonin)
5-HT _{2A} receptor	5-hydroxytryptamine (serotonin) receptor subtype 2A
5-HT _{2C} receptor	5-hydroxytryptamine (serotonin) receptor subtype 2C
ABC	Aberrant Behavior Checklist
ABC-I	Aberrant Behavior Checklist–Irritability
AC-279	N-desmethyl-pimavanserin, major metabolite of pimavanserin
ADHD	attention-deficit hyperactivity disorder
ADI-R	Autism Diagnostic Interview–Revised
AE	adverse event
ASD	autism spectrum disorder
ASR	accurate symptom reporting
AUC	area under the plasma concentration-time curve
AUC_{τ}	area under the plasma concentration-time curve during any dosing interval at steady state
BMI	body mass index
CDC	Centers for Disease Control and Prevention
CGI-I	Clinical Global Impression–Improvement
CGI-S	Clinical Global Impression–Severity
CGSQ	Caregiver Strain Questionnaire
CFR	Code of Federal Regulations
C _{max}	maximum (peak) observed drug concentration
C _{max-ss}	C _{max} at steady state
COVID-19	coronavirus disease 2019
C-SSRS	Columbia–Suicide Severity Rating Scale
DSM-5	Diagnostic and Statistical Manual of Mental Disorders, Fifth Edition
DSMB	data and safety monitoring board
DSM-IV	Diagnostic and Statistical Manual of Mental Disorders, Fourth Edition
EC	ethics committee
ECG	electrocardiogram
eCRF	electronic case report form
EDC	electronic data capture
EOT	end of treatment
ESRS-A	Extrapyramidal Symptom Rating Scale–Abbreviated

Term	Definition
ET	early termination
FDA	Food and Drug Administration
GCP	Good Clinical Practice
HbA _{1c}	glycosylated hemoglobin
HDL	high-density lipoprotein
HIV	human immunodeficiency virus
ICF	informed consent form
ICE	intercurrent event
ICH	International Council for Harmonisation
IRB	institutional review board
LAR	legally acceptable representative
MINI-KID	Mini International Neuropsychiatric Interview for Children and Adolescents
MMRM	mixed-effect model repeated measures
NSA-16	Negative Symptom Assessment–16
PANSS	Positive and Negative Syndrome Scale
PDP	Parkinson's disease psychosis
PK	pharmacokinetic(s)
PK/PD	pharmacokinetic/pharmacodynamic
QD	once daily
QRS	QRS interval on ECG
QT	QT interval on ECG
QTc	corrected QT interval on ECG
QTcB	corrected QT interval using Bazett's correction method
QTcF	corrected QT interval using Fridericia's correction method
RBS-R	Repetitive Behavior Scale–Revised
SAE	serious adverse event
SAP	statistical analysis plan
TEAE	treatment-emergent adverse event
ULN	upper limit of normal
US	United States
VABS	Vineland Adaptive Behavior Scales

Final Version: 1.0 Date: 21 December 2022

1 INTRODUCTION

This document is a research protocol and the described study will be conducted in compliance with the protocol, the International Council for Harmonisation (ICH) Good Clinical Practice (GCP) Guideline, and applicable regulatory requirements.

